### 9.4 Variables

**Exposures:** Maternal MS and related medication exposure before and during pregnancy are the basis of the exposure status of the study subjects in this study.

Pregnancies are considered unexposed if no MSDMDs of interest have been used within three months (except six months for mitoxantrone and cladribine) prior to LMP or during pregnancy. As the maximum reimbursable amount per purchase is the supply for three months of treatment, a pregnancy is defined as unexposed to MSDMDs if there are no purchases of MSDMDs within six months (except nine months for mitoxantrone and cladribine) prior to LMP or during pregnancy. Otherwise a pregnancy is defined as exposed to MSDMDs. Similarly, a pregnancy is defined as unexposed to IFN- $\beta$  if there have been no purchases of IFN- $\beta$  containing medications within six months prior to LMP or during pregnancy and otherwise a pregnancy is defined as exposed to IFN- $\beta$ .

The following MSDMDs and their ATC codes are included in this study: IFN- $\beta$ -1a (L03AB07), IFN- $\beta$ -1b (L03AB08), Peg IFN- $\beta$ -1-a (L03AB13), human normal immunoglobulin (J06BA02), cyclophosphamide (L01AA01), methotrexate (L01BA01, L04AX03), cladribine (L01BB04), mitoxantrone (L01DB07), alemtuzumab (L01XC04), glatiramer acetate (Copaxone®) (L03AX13), leflunomide (L04AA13), natalizumab (L04AA23), fingolimod (L04AA27), teriflunomide (L04AA31), azathioprine (L04AX01), dimethyl fumarate (N07XX09).

**Table 3: More detailed information on individual MSDMD agents, including information on availability and reimbursement in FIN, SWE and NOR.**

MSDMD agent	ATC code	Reimbursed in FIN in Jan 2015 (yes / no) 	Marketing authorisation date			Administration in hospital only 
			FIN	SWE	NOR	
IFN- $\beta$ natural	L03AB02		no	no	no	
IFN- $\beta$ -1-a	Avonex ®	yes	13.3.1997	13.3.1997	5.7.2002	no
	Rebif ®		4.5.1998	4.5.1998	19.8.2003	no
IFN- $\beta$ -1-b	Betaferon ®	yes	30.11.1995	30.11.1995	1.9.2006	no
	Extavia ®		20.5.2008	20.5.2008	20.5.2008	no
Peg IFN- $\beta$ -1-a	Plegridy ®	yes	18.7.2014	18.7.2014	18.7.2014	no
intravenous immunoglobulin	J06BA02	no	16.10.1991	10.10.1981	9.10.1996	yes
cyclophosphamide	L01AA01	no	4.6.1986	28.4.1959	6.4.1959	injection yes tablet no
methotrexate	L01BA01	yes  / no 	25.2.1981	23.6.1964	14.4.1971	tablet no
	L04AX03					infusion yes injection yes/no 
cladribine	L01BB04	no	25.9.2000	19.11.1993	14.11.1996	injection no infusion yes
mitoxantrone	L01DB07	no	30.8.1993	29.10.1987	1.8.1988	yes
alemtuzumab	L01XC04	no	12.9.2013	no	no	yes
glatimer acetate (Copaxone ® )	L03AX13	yes	8.3.2004	21.9.2001	24.2.2004	no 
leflunomide	L04AA13	yes	2.9.1999	2.9.1999	5.11.2004	no
natalizumab	L04AA23	no	27.6.2006	27.6.2006	27.6.2006	yes
fingolimod	L04AA27	yes	17.3.2011	17.3.2011	17.3.2011	no
teriflunomide	L04AA31	yes	26.8.2013	26.8.2013	26.8.2013	no
azathioprine	L04AX01	yes	31.1.1968	14.3.1968	9.8.1968	no
dimethyl fumarate	N07XX09	no	30.1.2014	30.1.2014	30.1.2014	no

-  Information on only reimbursed medication can be acquired from the National Prescription Register in Finland.
-  Pre-filled syringes/pens and tablets.
-  Injection and infusion solutions - except Trexan injection solution, which is reimbursed.
-  Information on drug use in hospitals and outpatient clinics are not collected in the Prescription Registers and thus information on exposure to these types of medication is not available.
-  Some of the injections are given in hospital and some can be self-administered at home.
-  Earlier there may have been also products that have been administered in hospital.
-  Sources (accessed on 3.2.2015):  
[http://www.ema.europa.eu/ema/index.jsp?curl=pages/medicines/landing/epar\\_search.jsp&mid=WC0b01ac058001d124](http://www.ema.europa.eu/ema/index.jsp?curl=pages/medicines/landing/epar_search.jsp&mid=WC0b01ac058001d124),  
<http://www.fimea.fi/laaketieto/valmisteyhteenvetot/laakkeet>  
<http://www.lakemedelsverket.se/LMF>  
<http://www.legemiddelverket.no/Legemiddelsoek/>

**Outcome variables:** The primary (P), secondary (S) and exploratory (E) outcomes are presented here according to pregnancy timeline.

Ectopic pregnancies (S) (ICD-10: O00) and spontaneous abortions (S) (ICD-10:O03):

- Information will be obtained from Patient Register (FIN, SWE, NOR) based on hospital visits due to these diagnoses

Elective termination of pregnancy (P) (ICD-10: O04):

- Information will be obtained from the DPP (FIN) and from MBR (NOR), where the abortions are registered from GW 12.
- This information is not available from SWE.

Stillbirth (P):

- Information will be obtained from the DPP (FIN) and MBR (SWE, NOR). The Finnish DPP and Norwegian MBR include information on all stillbirths of fetuses with a birth weight of at least 500 g or with a gestational age of at least 22+0 GW. The Swedish MBR includes data on stillbirths after 28 GW.

Live Birth (P):

- Information on live births will be obtained from the DPP (FIN) and MBR (SWE, NOR)

MCAs (P):

- Information will be obtained from the DPP (FIN), Patient Register (SWE) and MBR (SWE, NOR). The study will concentrate on MCAs. These outcomes are registered according to ICD-9 classification into 25 groups (ICD-codes 740-759). Minor anomalies will principally be excluded according to the European Surveillance of Congenital Anomalies (EUROCAT).

Defect cases (E):

- Information will be obtained from the DPP (FIN), Patient Register (SWE) and MBR (SWE, NOR). Defect cases with 3 or more minor anomalies will be defined according to the European Surveillance of Congenital Anomalies (EUROCAT).

Serious adverse pregnancy outcome (P):

- A composite endpoint including presence of elective TOPFA, MCA or stillbirth.

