**Population:** The target study population consists of Finnish, Swedish and Norwegian women diagnosed with MS who have been pregnant during the study period from 1996 to 2014. The pregnancy may have resulted in an induced abortion, spontaneous abortion, ectopic pregnancy, stillbirth, or live birth during the study period. A pregnancy will be considered unexposed if exposure is stopped at least three months prior to LMP (exceptions: six months for mitoxantrone and cladribine). MSDMDs that will be considered aside from IFN  $\beta$ -1a, IFN  $\beta$ -1b and Peg IFN- $\beta$ -1-a: human normal immunoglobulin (Anatomical Therapeutic Chemical (ATC) code, J06BA02), cyclophosphamide (L01AA01), methotrexate (L01BA01, L04AX03), cladribine (L01BB04), mitoxantrone (L01DB07), alemtuzumab (L01XC04), glatiramer acetate (Copaxone®) (L03AX13), leflunomide (L04AA13), natalizumab (L04AA23), fingolimod (L04AA27), teriflunomide (L04AA31), azathioprine (L04AX01), dimethyl fumarate (N07XX09).

**Comparisons:** The primary comparisons will be performed between the following study cohorts:

- i) women with MS exposed to IFN- $\beta$  (but not to other MSDMDs) (cohort 1) and women with MS unexposed to any MSDMDs (cohort 3), and,
- ii) women with MS exposed to IFN- $\beta$  (but not to other MSDMDs) (cohort 1) and women with MS unexposed to IFN- $\beta$  regardless of exposure to other MSDMDs (cohort 4).

**Outcomes:** The primary outcome variable is a serious adverse pregnancy outcome, which is defined as a composite endpoint including elective TOPFA, MCA, or stillbirth. Other outcome variables include live births, stillbirths, elective TOPFA or elective termination due to other reasons, MCA, spontaneous abortions, ectopic pregnancies, and several other perinatal adverse health outcomes.

**Data sources:** The study database will be constructed from the Nordic health registers: Drugs and pregnancy Project (DPP) (FIN), Patient Registers, MS Registers, Prescription Registers, Medical Birth Registers (MBRs), Malformation Register, Causes of Death Register, and Population Registers.

**Study size:** The estimated number of pregnancies in MS patients is 1671, encompassing data from:

- i) FIN: 1 January 1996 – 31 December 2014;
- ii) SWE: 1 July 2005 – 31 December 2014;
- iii) NOR: 1 January 2004 – 31 December 2014.

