#### **Prescription Registers (FIN, SWE, NOR)**

Information on maternal MSDMD exposure before and during pregnancy will be obtained from the Prescription Registers based on reimbursed drug purchases (information is linked to DPP in FIN). The Prescription Registers contain information on outpatient medication purchases in pharmacies (established FIN 1994, SWE 2005, NOR 2004). Prescription-only medicines are only sold in pharmacies, and dispensing requires a prescription issued by a physician or a dentist in FIN, SWE and NOR. In FIN, the register contains information on all purchased prescribed medicines that are reimbursed by the government. This excludes, for instance, most contraceptives. In SWE and NOR, all prescribed medicines purchased in community pharmacies are included irrespective of reimbursement status. The prescription data in the registers includes patient's ID, the generic name of the drug, ATC code, the brand name, the formulation and package, the amount as the defined daily dose (DDD), the date of purchase, the prescribing practice (primary vs. secondary healthcare), and the prescribing physician's area of specialisation.

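### The six-month purchase rule credits every purchase with the maximum three-month supply, so shorter supplies can put pregnancies that meet the protocol's own unexposed definition into cohorts 1 and 2, and no sensitivity analysis tests this

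*Protocol*

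**What the plan says.** The concept is stated in terms of use. The abstract (section 4, Population) has: "A pregnancy will be considered unexposed if exposure is stopped at least three months prior to LMP". Section 9.4 (Exposures) repeats it: "Pregnancies are considered unexposed if no MSDMDs of interest have been used within three months". Both make an exception of six months for two named agents.

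Section 9.4 then turns use into purchases, giving as its reason: "As the maximum reimbursable amount per purchase is the supply for three months of treatment". The resulting rule is: "a pregnancy is defined as unexposed to MSDMDs if there are no purchases of MSDMDs within six months". Everyone else falls on the other side: "Otherwise a pregnancy is defined as exposed to MSDMDs". The same six-month purchase rule is then stated for IFN-β alone, so it decides membership of cohorts 1 to 4 and both primary comparisons.

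On the data, section 9.3.1.1 (Prescription Registers) lists among the recorded fields "the amount as the defined daily dose (DDD), the date of purchase". For Sweden and Norway it adds that "all prescribed medicines purchased in community pharmacies are included irrespective of reimbursement status".

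**The concern.** Three months is the most that one reimbursed purchase can cover, not the amount each woman received. Adding it to every purchase extends the look-back by the same length whatever was dispensed. A woman whose last purchase was small and early in the six-month window can satisfy the use-based definition of unexposed and still be counted in cohort 1 or 2.

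The study asks whether IFN-β harms pregnancy. If such women carry the unexposed risk, their presence in the small exposed cohort moves the RR towards 1, which is the direction that hides harm. Section 9.7.6 does not vary the pre-LMP window or use supply length. Its MCA analysis of exposure up to the end of the first trimester still counts exposure before pregnancy, so these women stay in. Section 9.9 discusses exposure misclassification only for drugs given in hospitals and other institutions.

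**Working it through.** **1. When the two rules agree.** Let a purchase be made t months before LMP and last s months if used as dispensed. Supply reaches the three-month pre-LMP window only if t ≤ 3 + s. The protocol uses t ≤ 6.

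| Supply s | Matching look-back 3 + s | Last-purchase band exposed by the rule but not by the definition |
|---|---|---|
| 3 months | 6 months | none |
| 2 months | 5 months | 5 to 6 months before LMP |
| 1 month | 4 months | 4 to 6 months before LMP |

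If s exceeds 3, or stock is carried over from earlier purchases, the error reverses: a last purchase more than six months before LMP could still be in use inside the window.

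**2. Reproduce the plan's figure.** Inputs from section 9.5: cohort 1 n = 294, cohort 3 n = 1270, baseline p0 = 24/331 = 0.0725, two-sided 5%, power 80%, stated minimum detectable RR 1.72. The formula uses pooled variance under the null (SE0) and unpooled under the alternative (SE1): power = Φ[(p1 − p0 − 1.96·SE0)/SE1].

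At RR 1.72, p1 = 0.1247, the pooled proportion is 0.0823, SE0 = 0.01779 and SE1 = 0.02060. Then (0.0522 − 0.0349)/0.02060 = 0.84, and power = 80%. Solving for 80% gives RR 1.720 (1.717 with 7.3%). The stated 1.72 is right.

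**3. Effect of dilution.** Let m be the share of cohort 1 whose supply ended before the window. The documents give neither pack sizes nor the timing of last purchases, so m is an assumption. Assume also that these women have the baseline risk.

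- Observed RR = 1 + (1 − m)(1.72 − 1). For m = 10%: 1 + 0.9 × 0.72 = 1.65.
- True RR needed for 80% power under the rule = 1 + 0.72/(1 − m). For m = 10%: 1 + 0.72/0.9 = 1.80.
- If these women are moved to cohort 3: cohort 1 = 294(1 − m), cohort 3 = 1564 − cohort 1, and the step 2 formula is solved again.

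| m (assumed) | Observed RR | Power, rule as written | RR needed, rule as written | Cohort sizes after moving | RR needed after moving |
|---|---|---|---|---|---|
| 5% | 1.68 | 77% | 1.76 | 279 / 1285 | 1.73–1.74 |
| 10% | 1.65 | 73% | 1.80 | 265 / 1299 | 1.75 |
| 20% | 1.58 | 64% | 1.90 | 235 / 1329 | 1.79 |

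The 1.73–1.74 reflects a baseline of 7.3% or 24/331. Moving women shrinks cohort 1, so the fair comparison is column 4 with column 6: a gain in detectable RR of about 0.02–0.03, 0.05 and 0.11.

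**The case against.** The rule is a stated, reasoned choice. Section 9.4 moves openly from use to purchases and takes an upper bound on supply. A generous look-back protects the unexposed cohorts, and the prevalence in women unexposed to IFN-β is what the CHMP asked for (sections 7 and 8). Some loss of purity in the exposed group is the usual price. This stands: a reader might infer that the protocol assumes every purchase is a three-month supply, or that it contradicts itself unawares, and the text supports neither.

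A reader might also call the affected women truly unexposed. The registers record purchases, not injections. Missed or delayed doses and leftover stock can carry use into the window, so the claim holds only if the drug was used as dispensed. For the same reason, a supply-based rule is itself approximate and could move exposed women into the reference cohort. That argues against making it the primary rule.

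Nor do the documents show that the reverse error happens. They do not show that the reimbursement ceiling binds in Sweden and Norway, but they also give no instance of a longer supply or of stockpiling. It is a possibility only.

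Finally, section 9.7 leaves detail to a separate analysis plan. The cohort definition, however, is fixed here, and sections 9.7.6 and 9.9 list sensitivity analyses and limitations without touching supply length.

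**Conclusion.** The point holds in a limited form. The purchase rule reproduces the three-month use definition only for three-month supplies. Shorter ones can bring pregnancies that meet the unexposed definition into cohorts 1 and 2 and bias the RR towards 1, and nothing planned in the protocol would reveal it.

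The size is unknown. At an assumed 5% to 20% of cohort 1, and with baseline risk in those women, a true RR of 1.72 shrinks to between 1.68 and 1.58. The net gain from reclassifying them is small unless the share is large. It would be tempting to conclude that the sample-size figure is wrong, that the primary result is materially biased, or that the primary exposure rule must be replaced. The documents support none of these: 1.72 reproduces, and the distribution of dispensed amounts is not given. What is justified is a check, because it is cheap and concerns a bias in the unsafe direction for a safety study.

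**What to change.** Keep the six-month purchase rule as the primary definition. Add to section 9.7.6 a sensitivity analysis of primary objective 2 that:

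- computes end of supply from purchase date and dispensed amount in DDDs, carrying unused supply forward;
- classes a pregnancy as exposed if supply extends to or beyond the start of the protocol's own pre-LMP window, or if there is a purchase during pregnancy;
- reports how many pregnancies change cohort, by country.

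The phrase about extending to or beyond the start matters. Requiring the end date to fall inside the pre-LMP window would miss a three-month supply bought one month before LMP, which runs two months past LMP and may have no later purchase.

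Name the dispensed amount explicitly in the data request. Section 9.3.1.1 says the registers hold it, but section 6 places permit applications one month after the 31 October 2015 reference date, later than this version of 18 August 2015, so it should not be treated as already requested.

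The cost is one requested field, one derived variable and one repeat of the primary models. The drawback is that DDD-based supply is approximate when doses are missed or delayed, which is why it sits beside the purchase rule and does not replace it.

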### 9.2.4 Follow-up time

The cohort entry date (i.e. index date) is the date of LMP. This date is considered as the beginning of the pregnancy. The pregnancies are followed until induced abortion or birth. The births are followed-up for a maximum of 12 months for registration of MCAs (see section 9.2.3 Study period). Information on LMP, or gestational age, is not available for ectopic pregnancies or spontaneous abortions. The date of hospitalisation due to these outcomes will be used as a proxy of index date for these outcomes.

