The estimated background prevalence for the composite endpoint of serious adverse pregnancy outcome, consisting of TOPFAs, live births with MCA and all stillbirths, was 6.5% (personal communication with [name], THL, 15 May 2014) and 7.3% (= 24/331, based on the feasibility study in Finland, cf. Annex 1) in women with MS unexposed to IFN- $\beta$  (regardless of exposure to other MSDMDs) and unexposed to any MSDMD, respectively. Because these numbers best correspond to the study setting, they were taken as the most relevant baseline prevalences of serious adverse pregnancy outcomes in the sample size calculations. Lower outcome prevalences were investigated to test how sensitive the findings of minimum detectable effect sizes are to these assumptions. For comparison, in the Finnish feasibility study the prevalence of serious adverse outcomes was 3.7% = (38384/1031778) among all women, and according to EUROCAT 2015, the prevalence of malformation outcome among all women in the EU is 2.6%. The anticipated sample sizes in study cohorts 1-6 are:

- Cohort 1: 294 (80% of 368) for MS pregnancies exposed only to IFN- $\beta$ .
- Cohort 2: 368 (22% of 1671) for MS pregnancies exposed to IFN- $\beta$  regardless of exposure to other MSDMDs.
- Cohort 3: 1270 (76% of 1671) for MS pregnancies unexposed to any MSDMD.
- Cohort 4: 1303 (78% of 1671) for MS pregnancies unexposed to IFN- $\beta$ .
- Cohort 5: 33 (Cohort 4 size – Cohort 3 size = 1303 – 1270 = 33) for MS pregnancies exposed to MSDMDs except IFN- $\beta$  or glatiramer acetate (Copaxone®) or dimethyl fumarate (Tecfidera®).
- Cohort 6: Approximately 2.9 Million pregnancies for women from the general population in FIN, SWE and NOR without MS diagnosis based on the based on the feasibility study (cf. Annex 1).

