With these sample sizes and baseline outcome prevalence, the minimum detectable effect size between the MS women exposed to IFN- $\beta$  only (cohort 1) vs. MS women unexposed to any MSDMDs (cohort 3) is 1.72 in terms of RR using 80% power and a 5% two-sided significance level. If the background prevalence calculated among MS pregnancies unexposed to any MSDMD's would be closer to that in the whole population, e.g. 6%, 5%, 4% or 3%, the respective minimum detectable effect sizes would be 1.81, 1.91, 2.04, and 2.23. Regarding the comparison of a composite serious adverse pregnancy outcome between women with MS exposed to IFN- $\beta$  only (cohort 1) vs. unexposed to IFN- $\beta$  regardless of exposure to other MSDMDs (cohort 4), the minimum detectable effect size (RR) is approximately 1.77. Regarding the comparison of the composite serious adverse pregnancy outcome between women with MS exposed to IFN- $\beta$ s regardless of exposure to other MSDMDs (cohort 2) vs. unexposed to any MSDMD (cohort 3), the minimum detectable effect size (RR) is approximately 1.66.

The sample size calculations were performed using the `bpower` function of the R programming language (<http://www.r-project.org>).

**Table 5: The estimated numbers of all MS pregnancies and MS pregnancies unexposed to IFN- $\beta$ s available for the study during the study period by country.**

Country and study period		ALL MS Pregnancies	MS Pregnancies unexposed to IFN- $\beta$ s 
Country	Study period	Number of pregnancies	Number of pregnancies
Finland	1 Jan 1996 – 31 Dec 2014	777 	606 
Sweden	1 Jul 2005 – 31 Dec 2014	482 	376 
Norway	1 Jan 2004 – 31 Dec 2014	412 	321 
TOTAL		1671	1303

1) Estimated as 433 from time period 1 Jan 1996 – 31 Dec 2010 plus 4\*86 MS pregnancies from four additional years 2011 – 2014 where 86 denotes the number of MS pregnancies in 2010

2) Estimated as 329 MS births from Jul 2005 – 31 Dec 2011 plus (329 / 6.5) MS births from three additional years 2012 – 2014.

3) Estimated as 330 MS births from 1 Jan 2004 – 31 Dec 2014 divided by (1-0.2) where 0.2 denotes the estimated abortion prevalence

4) Estimated as the number of ALL MS PREGNANCIES x 78% where 78% denotes the estimated proportion of MS pregnancies unexposed to IFN- $\beta$  regardless of exposure to other MSDMDs

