### 9.7.2 Denominators used for different pregnancy outcomes

The denominator used for the calculation of the descriptive statistics and prevalence of specific pregnancy outcomes in each study cohort varies by pregnancy outcome. Table 6 below describes how the denominators are defined for each pregnancy outcome.

**Table 6: Denominators used for calculation of the descriptive statistics and prevalence of pregnancy outcomes in each study cohort.**

Pregnancy outcome	Denominator used in each study cohort
Serious adverse pregnancy outcome	Number of elective terminations + number of births (still or live)
Elective TOPFA or other reasons	Number of elective terminations + number of births (still or live)
Still births	Number of elective terminations + number of births (still or live)
Live births	Number of elective terminations + number of births (still or live)
MCA	Number of elective terminations + number of births (still or live)
MCA in live births	Number of live births
Mode of delivery (CS/vaginal)	Number of live births, separately for single and multiple pregnancies
Preterm birth	Number of live births, separately for single and multiple pregnancies
Birth weight, LBW and birth weight, head circumference for gestational age	Number of live births, separately for single and multiple pregnancies
Sex of the newborn	Number of live births, separately for single and multiple pregnancies
Head circumference, low head circumference	Number of full-term live births, separately for single and multiple pregnancies
Apgar scores	Number of full-term live births, separately for single and multiple pregnancies
Ectopic pregnancies	Number of all pregnancy events
Spontaneous abortions	Number of all pregnancy events
Defect cases	Number of elective terminations + number of births (still or live)

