### 9.7.3 Analysis of primary objectives

With regard to objective #1, the descriptive statistics including the number of events (n) and prevalence (%) will be presented for each pregnancy outcome (i.e. serious adverse pregnancy outcome, elective TOPFA, MCA, stillbirth, and live birth) in each study cohort separately and also for the whole study population. Information on live births, stillbirths and TOPFAs will be included in the analyses of MCA, as approximately 10% of MCAs are detected in foetuses of TOPFA.

With regard to objective #2, the prevalence of the serious adverse pregnancy outcomes will be compared between the study cohorts using log-binomial regression. Two models, base and adjusted, will be used in these comparisons. The base model will be adjusted for the following design variables and *a priori* likely confounders: country, year of pregnancy outcome, maternal age at LMP, number of previous pregnancies, any chronic diseases, and exposure to any teratogenic medications including steroids.

The adjusted model will be built using a variable selection procedure (Bursac et al. 2008). Candidate covariates for the adjusted model will be those in the base model and the following additional ones: university hospital district, pre-pregnancy weight, pre-pregnancy BMI, number of previous abortions, smoking status during pregnancy, number of foetuses in pregnancy (single vs. multiple), time since MS diagnosis and duration of MS treatment as available in the data sources. Variable selection starts by applying first the unadjusted model and proceeds as follows:

1. Each candidate covariate will be considered a potential confounder if the univariate association between the covariate and the serious adverse pregnancy outcome, tested with the Wald test for logistic regression with *P*-value cut-point of 0.25.
2. All candidate covariates identified as potential confounders in step 1 will be added simultaneously to the model. After this, additional covariates not identified as potential confounders in step 1 will be added to the model one at a time and the model fit comparing each null vs alternative model will be assessed by the likelihood-ratio test. Variables in the alternate model will be retained at a likelihood ratio test of *P*-value <0.1.

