### 9.7.6 Sensitivity analyses

- Lack of information on terminations of pregnancy due to foetal anomalies from SWE may yield underestimation of the prevalence of MCA in the study population. In FIN, 10.5% of total cases with MCAs were diagnosed and recorded in TOPFAs between 1993 and 2010. However, this may bias the study results on MCAs if the risk for TOPFA differs between women with different MSDMD exposures or MS exposure in SWE. Separate analyses will be performed on MCAs for the Norwegian and the Finnish data including pregnancy terminations, stillbirths and live births, and another analysis including live births only. The analyses will also be stratified by country as the follow-up times of the newborn babies for recording the malformations in MBRs or Malformation Register may vary between the countries.

- Information on pregnancy terminations is available from GW 12 onwards from the Norwegian data, and therefore, information on early pregnancy terminations conducted before GW 12 could result in incomplete data. Therefore separate analyses by trimesters on pregnancy terminations will be performed.
- In additional sensitivity analyses on MCAs, outcomes will be assessed where exposure occurred prior to pregnancy and through to the end of the first trimester of pregnancy. Also, an analysis of MCA outcomes from live births only will be performed.
- As there is a geographical variation in MS prevalence not only between countries but also within countries, descriptive statistics will be conducted by country and university hospital district level. Country and region will also be included in the multivariate analyses.
- Possible changes in diagnostic criteria and developments in examination and treatment throughout time, as well as trends in obstetric care may influence the estimated prevalence. The study periods also vary between the countries, which may reflect the deviation in the results. Therefore the year of pregnancy outcome will be taken into account in the descriptive statistics and analyses. By taking into account the data from 1 Jan 2005 to 31 Dec 2014 from each country (time period in which the data is available i.e. overlaps for all 3 countries), a separate sensitivity analysis of the primary objective will be provided as well.

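### The IFN-beta exposure window stays open until the pregnancy ends, so its length depends on the outcome, and a first-trimester-window check is planned for MCAs only

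*Protocol*

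**What the plan says.** Under Exposures in section 9.4, a pregnancy is unexposed to IFN-beta if no purchase falls "within six months prior to LMP or during pregnancy and otherwise a pregnancy is defined as exposed". No gestational limit is set, so a purchase shortly before delivery counts the same as one before conception.

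On when the window closes, section 9.2.4 says: "The pregnancies are followed until induced abortion or birth".

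The primary outcome is described in section 9.4 as "A composite endpoint including presence of elective TOPFA, MCA or stillbirth". Table 6 in section 9.7.2 gives it a denominator of all elective terminations, whatever the reason, plus all still and live births. Stillbirth, live birth, MCA and elective termination share that denominator and are also compared under primary objective 2.

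For the model, section 9.7.3 says that "the prevalence of the serious adverse pregnancy outcomes will be compared between the study cohorts using log-binomial regression". Exposure enters as cohort membership. There is no landmark, time-dependent term or trimester limit.

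Section 9.7.6 plans one restricted-window analysis. It is confined to MCAs, whose "outcomes will be assessed where exposure occurred prior to pregnancy and through to the end of the first trimester of pregnancy". The analyses by trimester in sections 9.7.6 and 9.9 concern when terminations took place, not when the drug was bought.

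**The concern.** Follow-up starts at LMP, but cohort membership can be settled by something that happens months later, and only if the pregnancy is still going on. A term birth offers about 40 weeks after LMP in which one purchase moves it from cohort 3 or 4 into cohort 1. A pregnancy terminated in the first or early second trimester offers far fewer. This is the usual immortal-time problem: surviving to a late purchase is a condition of being classed as exposed by it.

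There is a second effect. A pregnancy whose only purchase falls after the first trimester cannot owe a structural anomaly to that purchase, yet it adds to the exposed denominator for the anomaly components. That dilutes any real effect.

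In a safety study both matter, because the result is meant to show whether exposure harms the pregnancy. The protocol sees the issue for MCAs but provides no check for the composite or the other primary outcomes.

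**Working it through.** **The plan's own figure.** Section 9.5 gives a minimum detectable RR of 1.72 for cohort 1 (294) against cohort 3 (1270), "using 80% power and a 5% two-sided significance level", with a background of 24/331 = 7.3%. A two-sided two-proportion normal approximation with pooled variance gives 1.720 with 24/331 and 1.717 with 7.3%. The figure reproduces.

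**The unknown.** Let f be the share of cohort 1 that is late-only: no IFN-beta purchase from six months before LMP to day 84 (the end of the first trimester in section 2), but at least one after it. The protocol gives no value. I assume 2% to 20%.

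**1. Events that end before a late purchase is possible, true RR = 1.** Let r be their rate. Late-only pregnancies have none of them. Cohort 1 then shows r(1−f). Cohort 3 has lost 294f event-free pregnancies and shows r(1270+294f)/1270. So

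RR = (1−f) / (1 + 294f/1270)

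- f = 2%: 0.98/1.0046 = 0.98
- f = 5%: 0.95/1.0116 = 0.94
- f = 10%: 0.90/1.0232 = 0.88

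The result does not depend on r. It is the limiting case for elective termination; terminations late enough to leave room for a purchase are affected less.

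**2. Live birth, true RR = 1.** Let t be the share of the denominator ending in such a termination, and ignore stillbirth. Then RR = [1 − t(1−f)] / [1 − t(1+294f/1270)]. With f = 5%, this is 0.905/0.8988 = 1.007 for t = 10% and 0.810/0.7977 = 1.015 for t = 20% (both t assumed).

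**3. Composite, true RR = 1.** Let p = 7.3%. Let q be the share of composite events, and s the share of non-events (terminations for other reasons), that end too early to be late-only. The event rate among late-only pregnancies is

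pL = p(1−q) / [p(1−q) + (1−p)(1−s)]

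and RR = [(1−f)p + f·pL] / {[p(1270+294f) − 294f·pL]/1270}.

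| q | s | f = 2% | f = 5% | f = 10% | f = 20% |
|---|---|---|---|---|---|
| 10.5% | 0 | 0.998 | 0.994 | 0.988 | 0.976 |
| 10.5% | 20% | 1.003 | 1.007 | 1.013 | 1.027 |
| 20% | 20% | 1.000 | 1.000 | 1.000 | 1.000 |
| 30% | 0 | 0.993 | 0.983 | 0.965 | 0.931 |

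The 10.5% is the Finnish share of MCA cases recorded in TOPFA (section 9.7.6), used as a rough stand-in. The other q and s values are assumed. The sign turns on how q compares with s, and the protocol fixes neither for the composite.

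**4. Dilution of the anomaly components.** Observed RR = (1−f)·RR + f. A true 1.72 is seen as 1.684 at f = 5% and 1.648 at f = 10%; power falls from 0.80 to 0.77 and 0.73. A true 1.0 stays 1.0. A true 0.7 rises to 0.715 and 0.73. The movement is toward the null, not always downward.

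**The case against.** The strongest reply is that the definition answers the stated question. Section 8 asks about exposure before or during pregnancy and defines the cohorts that way. A cut at day 84 would change the estimand of the primary analysis rather than correct an error. That stands, and it is why the remedy belongs among the sensitivity analyses.

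The late-only group may also be small. Section 7 says that starting IFN-beta in pregnancy is contraindicated, and a woman continuing treatment would normally have an earlier purchase. That also stands; only a count will settle it.

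A reader might infer that the primary RR is biased downward and that the drug will look safer than it is. The documents do not support that. Terminations for other reasons are short-window non-events in the same denominator and push the composite RR up. Sweden records no terminations, so the TOPFA route is absent there. Stillbirths are by definition at 22 weeks or later, or at least 500 g (after 28 weeks in the Swedish register), so their windows are fairly long. Later exposure may matter for stillbirth, so late purchases cannot be called irrelevant to the whole composite.

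The offset has limits too. Norway registers terminations only from week 12, so early terminations for other reasons come only from Finland, 777 of 1671 expected pregnancies. If 20% of the Finnish denominator were such terminations (assumed), they would make up about 0.20 × 777/1671 = 9% of the pooled one. A clear reversal therefore needs a large share, but the sign remains open.

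The offset does not apply to elective termination or live birth. For these, each early termination is respectively an event or a failure, so the direction is clear when the true RR is 1.

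**Conclusion.** The concern holds as a gap in the sensitivity analyses. Opportunity for exposure depends on the outcome, the fixed cohort label does not handle this, and the restricted-window check stops at MCAs.

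With a true RR of 1, the RR for elective termination is pushed down, to about 0.98, 0.94 or 0.88 in the limiting case at late-only shares of 2%, 5% or 10%, and the RR for live birth is pushed up by a smaller amount. For the composite, the calculations span about 0.965 to 1.013 for late-only shares up to 10%, so neither direction nor size is known. All of this rests on assumed values for the late-only share and for the shares of events and non-events that end early.

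This is a cheap improvement to the plan. It is not a demonstrated downward bias of the primary RR, and it does not require the primary exposure definition to be replaced.

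**What to change.** In section 9.7.6, extend the first-trimester-window analysis from MCAs to the composite, elective termination, stillbirth and live birth, for both primary comparisons:

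- Classify exposure on purchases from six months before LMP (nine for mitoxantrone and cladribine, as in section 9.4) to day 84.
- Keep pregnancies with purchases only after day 84 in the unexposed cohort. Removing them would again select on having lasted that long.
- Report the number of late-only pregnancies by cohort and outcome, so that the reader can judge whether the issue matters.
- For stillbirth, show the any-time result alongside, or treat a later first purchase as time-dependent.
- Add a run that uses pre-LMP purchases only, because the day-84 window is still cut short for terminations before day 84.

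The cost is one or two extra runs and a paragraph of text. LMP is available for births and terminations (section 9.9), and purchase dates are already needed for the present rule. Cohort 1 is slightly smaller in these runs: if 5% is late-only and moves to cohort 3, the minimum detectable RR goes from 1.717 to 1.732.
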